### Body Surface Area

A clinical estimation is made of the total BSA affected by AD. The surface area of the subject's right or left hand is designated as the measuring device, with the total surface of the palm and 5 digits assumed to be approximately equivalent to 1% of the subject's total BSA.

### Validated Investigator Global Assessment Scale for Atopic Dermatitis

The vIGA-AD ([Appendix N](#)) is a validated assessment instrument used in clinical studies to rate the severity of AD globally, based on a 5-point scale ranging from 0 (clear) to 4 (severe).

### SCORing Atopic Dermatitis

Study investigators will complete Components A and B of the SCORAD assessment ([Appendix F](#)) previously described. The extent of AD (Component A) is assessed as a percentage of each defined body area and reported as the sum of all areas, with a maximum score of 100%. Component B is the assessment of the severity of 6 specific symptoms of AD (redness, swelling, oozing/crusting, excoriation, skin thickening/lichenification, dryness) using the following scale: none (0), mild (1), moderate (2), or severe (3) (for a maximum of 18 total points). The SCORAD is calculated using the formula  $A/5 + 7B/2 + C$  (from the subject assessment), and the maximum score is 103. SCORAD Components A and B will not be on the electronic tablet; instead, they will be performed on paper worksheets and manually entered

into the eCRF. The rule of 9's method should be used to assess the percentage of each defined body area on the paper worksheets for Component A.

### COVID-19 Pandemic-Related Acceptable Protocol Modifications

Collection of investigator assessment data is not permitted by remote or virtual visits.

## 3.6 12-Lead Electrocardiogram

---

A 12-lead ECG will be performed at designated study visits specified in Section 2. The ECG should be performed prior to blood collection.

For subjects with a normal ECG taken within 90 days of Screening, a repeat ECG at Screening will not be required, provided all protocol-required documentation is available and nothing has changed in the subject's health status since the time of the test that warrants a repeat test.

The ECGs will be evaluated by an appropriately trained physician at the site ("local reader"). The local reader from the site will sign and date all ECG tracings and will provide his/her global interpretation as a written comment on the tracing using the following categories:

- Normal ECG
- Abnormal ECG – not clinically significant
- Abnormal ECG – clinically significant

Only the local reader's evaluation of the ECG will be collected and documented in the subject's source folder. The automatic machine reading (i.e., machine-generated measurements and interpretation that are automatically printed on the ECG tracing) will not be collected.

## 3.7 Height, Weight, and Waist Circumference

---

For the adult population, height will be measured at Screening only with shoes off. Body weight will be measured at scheduled visits specified in Section 2. The subject should wear lightweight clothing and no shoes during weighing. Waist circumference should be measured at Screening and Week 52; however, if missed at Screening it can be recorded at the Baseline (Study Day 0) visit.

For the adolescent population (as defined at Baseline), height, body weight, and waist circumference will be measured at Screening (however, if missed at Screening it can be recorded at the Baseline [Study Day 0]), Week 10, Week 28, and Week 52 with shoes off. The subject should wear lightweight clothing and no shoes during weighing.

## 3.8 Vital Signs

---

Vital sign determinations of systolic and diastolic blood pressure (BP), pulse rate, respiratory rate, and body temperature will be obtained at visits specified in Section 2. BP and pulse rate should be measured after the subject has been sitting for at least 3 minutes and before blood draws are performed.

## 3.9 Physical Examination

---

A complete physical examination will be performed at the designated study visits specified in Section 2. The physical examination performed on Study Day 0 will serve as the baseline physical examination for the entire study. If appropriate, a targeted physical exam should be performed at any other visit (e.g., to evaluate a reported adverse event). Any significant physical examination findings after the first dose will be recorded as AEs, while any findings prior to the first dose will be recorded as medical history. All findings, whether related to an AE or part of each subject's medical history, will be captured on the appropriate eCRF page.

## 3.10 Handheld ePRO Device

---

During the Screening Visit, subjects will be dispensed a handheld ePRO device to collect daily Worst Pruritus NRS, daily and weekly ADerm-SS, and daily and weekly ADerm-IS information. At each visit, site representatives should check to see that subjects have performed the required assessments between study visits. Data will be collected from the day of the Screening visit through the Week 16 visit.

## 3.11 Study Drug Administration

---

Study drug will be administered to subjects beginning at Baseline (Study Day 0) and as specified in Section 2.1. All subcutaneous (SC) doses of risankizumab and placebo will be administered by study site personnel under the direction of the investigator. The date and time (to the nearest minute) of onset of study drug administration will be recorded in the subject's medical record. The first dose of study drug will be administered after all other Baseline (Study Day 0) procedures are completed.

Study drug administration instructions for risankizumab pre-filled syringes will be provided for use by site staff.

### COVID-19 Pandemic-Related Acceptable Protocol Modifications

If a subject cannot travel to the site for a visit when study drug administration is planned, site personnel may travel to the subject's home to conduct an at-home visit. Study drug may be transported under

appropriate storage conditions and administered by trained site personnel. The site must contact the sponsor to obtain instructions on how to dispense drug in the IRT system for at-home visits.

If an at-home visit is scheduled, site staff should also bring the ePRO tablet to the home for the subject to complete those assessments, see Section 3.4 for more details.

### Monitoring for Hypersensitivity Reactions

Therapeutic protein products, such as biologics, may elicit a range of acute effects, from symptomatic discomfort to sudden, fatal reactions that have often been grouped as "infusion or injection reactions" in the past. Although the term implies a certain temporal relationship, infusion or injection reactions are otherwise not well defined and may encompass a wide range of clinical events, including anaphylaxis and other events that may not be directly related to antibody responses, such as cytokine release syndrome.

In the event of a suspected systemic hypersensitivity/anaphylactic reaction, in addition to the standard AE eCRF, a supplemental Hypersensitivity Reactions eCRF should also be completed by the site. The clinical criterion for diagnosing anaphylaxis is provided in [Appendix O](#) for reference; symptoms of anaphylactic reaction usually occur within 24 hours after exposure to an allergen. These are guidelines that are used to help diagnose anaphylaxis. The investigator is encouraged to report any suspected reactions.

Subjects should be closely monitored for signs and symptoms of hypersensitivity reactions, including allergic reactions and anaphylaxis, for approximately 2 hours after study drug administration at the Baseline/Study Day 0 and Week 16 visits, and 1 hour after all other doses of study drug (dosing visits other than the Study Day 0 and Week 16 visits). A medical person qualified in the treatment of acute hypersensitivity reactions must be present during the injections.

All appropriate medical support measures (e.g., diphenhydramine, steroids, epinephrine, oxygen) for the treatment of suspected hypersensitivity reactions should be available for immediate use in the event that a suspected hypersensitivity reaction occurs. Subjects who manifest any new signs or symptoms during the injection should be monitored for appropriate resolution prior to leaving the site. Subjects are encouraged to report any symptoms related to a possible injection-related reactions or local injection site reaction or late phase reactions to the site any time during the study. A patient information card listing the symptoms of these reactions will be provided to the participants.

In the event of a suspected anaphylactic reaction, blood and serum samples should also be collected as described in Section 3.12.

### 3.12 Clinical Laboratory Tests

A certified laboratory will be utilized to process and provide results for the clinical laboratory tests. Laboratory reference ranges will be obtained prior to the initiation of the study. The baseline laboratory test results for clinical assessment for a particular test will be defined as the last measurement prior to the initial dose of study drug.

Instructions regarding the collection, processing, and shipping of these samples will be provided by the central laboratory.

If a laboratory test value is outside the reference range and the investigator considers the laboratory result to be clinically significant, the investigator will:

- repeat the test to verify the out-of-range value;
- follow the out-of-range value to a satisfactory clinical resolution; or
- discontinue the subject from the study or require the subject to receive treatment; in this case, the laboratory result will be recorded as an adverse event.

Clinical Laboratory Tests		
HEMATOLOGY	CLINICAL CHEMISTRY	URINALYSIS
Hematocrit Hemoglobin Red Blood Cell (RBC) count/ Erythrocytes Mean Corpuscular Volume (MCV) White Blood Cell (WBC) count/ Leukocytes Platelet count/Thrombocytes Diff. Automatic (absolute count): Neutrophils Eosinophils Basophils Monocytes Lymphocytes Manual Differential (ONLY IF Automated Differential is abnormal): Neutrophils, bands (Stabs) Neutrophils, polymorphonuclear Eosinophils Basophils Monocytes Lymphocytes	Electrolytes Calcium Sodium Potassium Chloride Bicarbonate Substrates Glucose Blood urea nitrogen (BUN) Creatinine Estimated glomerular filtration rate (eGFR) Bilirubin Total Bilirubin Direct (if total is elevated) Bilirubin Indirect (if total is elevated) Albumin High-sensitivity C-Reactive Protein (hsCRP) Cholesterol, total a LDL Cholesterol a HDL Cholesterol a Triglycerides a FSH b	Dipstick Urinalysis Urine Nitrite Urine Protein Urine Glucose Urine Ketone Urobilinogen Urine Bilirubin Urine RBC/Erythrocytes Urine WBC/Leukocytes Urine pH Urine creatinine Urine Sediment (microscopic examination, only if urine analysis abnormal) Urine Sediment Bacteria Urine Cast in Sediment Urine Squamous Epithelial Cells Urine Sediment Crystals, Unspecified Urine Sediment RBC/Erythrocytes Urine Sediment WBC/Leukocytes Urine Urine Albumin-to-Creatinine Ratio (UACR)

Clinical Laboratory Tests		
Coagulation: International Normalized Ratio (INR) c	Enzymes Alanine aminotransferase (ALT) Aspartate aminotransferase (AST) Alkaline Phosphatase (AP) Gamma-glutamyl transferase (GGT/ $\gamma$ -GT) Creatine Kinase (CK) Only if CK is elevated: Troponin (point-of-care) OR Troponin (central lab) + CK-MB	
INFECTION SCREENING		PREGNANCY TESTINGe
Hepatitis B surface antigen (HBs Ag) (qualitative) d Hepatitis B surface antibody (HBs Ab) (qualitative) d Anti-Hepatitis B core (HBc) total (qualitative) d Hepatitis B Virus (HBV) DNA (quantitative) d Anti-Hepatitis C Virus (HCV) (qualitative) d HCV RNA (quantitative) d HIV 1 and HIV-2 Ab (qualitative) d QuantiFERON ® -TB (or Interferon gamma release assay [IGRA] equivalent) and/or purified protein derivative (PPD)		Urine Pregnancy test (local) f Serum Pregnancy test g
		PK/IMMUNOGENICITY
	ADDITIONAL TESTING	Serum risankizumab concentration Serum ADA Serum nAb
	IgE	ANAPHYLAXIS TESTINGh
		Serum risankizumab concentration i ADA i nAb i Tryptase j Histamine

- Performed only at Baseline visit (following a minimum 8-hour fast).
- FSH testing is to be done at Screening in all women aged  $\leq 55$  years with no menses for 12 or more months without an alternative medical cause.
- INR test only performed if ALT or AST  $> 3 \times$  ULN (upper limit of normal).
- Performed only at Screening.
- Pregnancy testing is not required for female subjects of non-childbearing potential (defined in protocol).
- Urine pregnancy test will be performed at every dosing visit and the Week 52/PD Visit and must be conducted prior to study drug dosing. Negative urine pregnancy test results must be confirmed prior to study drug dosing.
- Serum pregnancy test is conducted at Screening and at other visits only if urine pregnancy test is positive. Negative serum pregnancy test results must be confirmed prior to study drug dosing.
- Only performed in case of a suspected anaphylactic reaction.
- PK and ADA/nAb samples drawn in context of a suspected anaphylactic reaction are collected in addition to those collected at scheduled time points for PK/immunogenicity and are only collected if a suspected anaphylactic reaction occurs while at the study site.
- A follow-up tryptase level should be collected a minimum of 2 weeks after any suspected anaphylaxis event.

## Pregnancy Tests (Serum and Urine)

A pregnant or breastfeeding female will not be eligible for participation or continuation in this study.

Pregnancy testing should not be performed for postmenopausal women.

A serum pregnancy test will be performed at Screening and a urine pregnancy test will be performed at Baseline for all female subjects. The serum pregnancy test will be sent to and performed by the central laboratory. If the serum pregnancy test is positive, the subject is considered a screen failure. If the serum pregnancy test is borderline, it should be repeated to determine eligibility.

If the repeat serum pregnancy test is:

- Positive, the subject is considered a screen failure;
- Negative, the subject can be enrolled into the study;
- Still borderline  $\geq 3$  days later, this will be considered documentation of continued lack of a positive result and the subject can be enrolled into the study in the absence of clinical suspicion of pregnancy and other pathological causes of borderline results.

Additional urine pregnancy tests for female subjects of childbearing potential will be performed at visits indicated in Section 2. More frequent pregnancy tests can be performed throughout the study at the investigator's discretion or if required per local/country requirements.

If the urine pregnancy test (which is performed at the site) is negative, begin or continue dosing. If the urine pregnancy test is positive, withhold dosing and perform a serum pregnancy test. Pregnant subjects must discontinue from the study.

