## 5 STUDY ACTIVITIES

### 5.1 Eligibility Criteria

---

Subjects must meet all of the following criteria in order to be included in the study. Anything other than a positive response to the questions below will result in exclusion from study participation.

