## Contraception

- ✓ 24. For all females of child-bearing potential, a **negative serum pregnancy test** at the Screening Visit and a negative urine pregnancy test at Baseline prior to the first dose of study drug.
- ✓ 25. **If female**, subject must be of non-childbearing potential OR a female of childbearing potential practicing at least 1 protocol-specified **method of birth control**, that is effective from Study Day 0 through at least 140 days (20 weeks or as guided by the local risankizumab label (if approved), whichever is longer) after the last dose of study drug (local practices may require 2 methods of birth control).
- ✓ 26. Female who is not **pregnant, breastfeeding, or considering becoming pregnant** during the study or for at least 140 days (20 weeks or as guided by the local risankizumab label (if approved), whichever is longer) after the last dose of study drug.

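### A persistently borderline Screening serum pregnancy test makes a woman ineligible under criterion 24 and not dosable under the laboratory-table footnote, yet enrollable and dosable under the pregnancy-test text of Operations Manual 3.12

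*Protocol*

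**What the plan says.** **Protocol 5.1, opening sentence.** Eligibility is all-or-nothing: "Anything other than a positive response to the questions below will result in exclusion from study participation".

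**Protocol 5.1, Contraception, criterion 24.** For all females of child-bearing potential it requires a "negative serum pregnancy test", with the timing and the second test given as "at the Screening Visit and a negative urine pregnancy test at Baseline prior to the first dose of study drug". The criterion has no borderline category.

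**Operations Manual 3.12, laboratory table, serum footnote (g).** After saying when the serum test is done (at Screening, and at other visits only if the urine test is positive), it adds: "Negative serum pregnancy test results must be confirmed prior to study drug dosing".

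**Operations Manual 3.12, Pregnancy Tests (Serum and Urine).** "If the serum pregnancy test is borderline, it should be repeated to determine eligibility". Three results of the repeat are then listed: positive, negative, and still borderline at least 3 days later. For the third, "this will be considered documentation of continued lack of a positive result and the subject can be enrolled into the study". A condition is attached, and the allowance holds only "in the absence of clinical suspicion of pregnancy and other pathological causes of borderline results". Later in the same text: "If the urine pregnancy test (which is performed at the site) is negative, begin or continue dosing".

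**The concern.** Screening for pregnancy is a safeguard that every site has to apply in the same way. Here a site can follow one operative instruction to the letter and break another. A site working from criterion 24 would exclude a woman whose serum result stays borderline. A site working from the pregnancy-test text could enrol her and give the first dose.

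If she is enrolled, she has not met an entry criterion. SAP Appendix A tabulates subjects who entered without satisfying entry criteria, and Protocol 5.9 prohibits deviations except to remove an immediate hazard. The site could therefore be recorded as deviating for doing what the Operations Manual told it to do.

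**Working it through.** No figure is involved, so the check sets the texts side by side.

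**Step 1: which repeat results conflict.** Take a female of child-bearing potential whose first Screening serum test is borderline.

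| Repeat serum result | Criterion 24 with the all-criteria rule | Pregnancy-test text, 3.12 | Agree? |
|---|---|---|---|
| Positive | Not eligible | Screen failure | Yes |
| Negative (repeat within Screening) | Serum requirement met | Can be enrolled | Yes |
| Still borderline at least 3 days later, no clinical suspicion of pregnancy, no other pathological cause | Not eligible, because the result is not negative | Can be enrolled | **No** |

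The conflict is confined to the third row.

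**Step 2: whether the pregnancy-test text redefines negative.** It does not. It lists negative and still borderline as separate results with separate consequences. It describes the second as a continued lack of a positive result, which is not the same as calling it negative. It therefore cannot serve as a definition of the word used in criterion 24.

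**Step 3: dosing.** Give the woman in the third row a negative Baseline urine test.

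- Serum footnote: dosing needs a confirmed negative serum result. She has none, so she may not be dosed.
- Pregnancy-test text: a negative urine test means dosing begins. Nothing there makes an exception for women enrolled on a borderline serum result, so she may be dosed.

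**Step 4: whether an order of precedence settles it.** The Operations Manual is Appendix F of the protocol, and Protocol 8.2 requires conduct in accordance with both. I found no statement of which prevails. Precedence would in any case leave the dosing conflict, because the footnote and the pregnancy-test text are both in Operations Manual 3.12.

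**Step 5: the urine test.** Criterion 24 requires a negative urine result at Baseline. The urine footnote of the laboratory table requires a confirmed negative urine result before dosing and places the test at every dosing visit. The pregnancy-test text withholds dosing on a positive urine result and calls for a serum test. These three agree, so the inconsistency concerns the serum result only.

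**The case against.** The best defence is that the pregnancy-test text is the working procedure for criterion 24. It says the repeat is done to determine eligibility, it belongs to an appendix of the protocol, and its allowance is conditional. The woman has had at least two serum tests, none positive, with the repeat at least 3 days later. She has no clinical suspicion of pregnancy and no other pathological cause, and she still needs a negative urine test before every dose. It can also be said that the serum footnote is aimed mainly at serum tests prompted by a positive urine test.

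Part of this stands. The conditions and the urine test limit the exposure risk, and a site that followed the procedure would be acting in good faith. It does not remove the conflict. The allowance contradicts criterion 24 precisely when its conditions are met, and the footnote names Screening among the times when the serum test is done. Even on the narrow reading of the footnote, the conflict on enrolment remains.

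A reader might infer three stronger things that the documents do not support:

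- *That the Baseline urine rule is also contradictory, with a negative serum result overriding a positive urine result.* The pregnancy-test text never says that a negative serum result releases dosing, and both criterion 24 and the urine footnote require a negative urine result.
- *That the documents disagree in substance on who is tested.* The pregnancy-test text does refer to all female subjects. The visit lists in Operations Manual 2.1 limit both the Screening serum test and the Baseline urine test to those of childbearing potential, and footnote e says that testing is not required otherwise. The sentence just before the loose wording also excludes postmenopausal women. This is untidy wording only.
- *That the allowance bypasses the pregnancy safeguard, with a size measured by the two Period A doses and the 140-day period after the last dose.* The Week 4 dose needs its own negative urine test, and the 140-day period applies to every woman of child-bearing potential, so neither figure measures this inconsistency.

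**Conclusion.** The inconsistency is real and narrow. A woman whose Screening serum result stays borderline, who meets the stated conditions and has a negative Baseline urine test, is ineligible under Protocol 5.1, not dosable under the serum footnote, and enrollable and dosable under the pregnancy-test text. The enrolment conflict rests on the plain wording alone. The dosing conflict rests on two readings: that the footnote covers the Screening serum test, as its own first sentence indicates, and that the general urine rule applies to women enrolled under the borderline allowance, since no exception is written.

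Few subjects are likely to be affected, and the documents give no rate from which to estimate how many. That sites would in fact treat such women differently, or that a given case would be logged as a deviation, is a foreseeable consequence rather than something the documents state. Endpoints, power and alpha do not depend on it. It should be corrected because it concerns possible exposure in pregnancy and the correction is cheap. The documents do not settle which rule is right, and this review takes no position on that.

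**What to change.** Reconcile Protocol 5.1 criterion 24, the serum footnote of the laboratory table in Operations Manual 3.12, and the pregnancy-test text of that section, so that a persistently borderline Screening serum result has one stated outcome for enrolment and one for dosing, worded the same way in all three places. The sponsor's medical team should decide the outcome.

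As a minor tidy-up in the same edit, bring the reference to all female subjects in the pregnancy-test text into line with the childbearing-potential wording in criterion 24, Operations Manual 2.1 and footnote e.

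The cost is a wording change to the protocol and its Operations Manual. It needs no new tests or visits and no change to the analysis. At most a few subjects would have a different eligibility outcome.

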## 5.5 Withdrawal of Subjects and Discontinuation of Study

---

A subject will be discontinued from study drug at any time for reasons including but not limited to the following:

- Clinically significant abnormal laboratory result(s) or AEs that preclude continuation of the study medication, as determined by the investigator and the AbbVie Therapeutic Area Medical Director (TA MD) (as applicable).
-

- The investigator believes withdrawal from the study is in the best interest of the subject.
- The subject requests withdrawal from the study.
- Eligibility criteria violation(s) are noted after the subject started study drug, if continuation of the study drug would place the subject at risk as determined by the AbbVie TA MD, after consultation with the investigator.
- Subject needs to initiate prohibited medication(s) or dosages, and continuation of the study drug would place the subject at risk as determined by the AbbVie TA MD.
- Subject is noncompliant with TB prophylaxis (if applicable) or develops active TB at any time during the study.
- Subject becomes pregnant while participating in the study.
- Subject is diagnosed with a malignancy. (Exception: localized NMSC or carcinoma in-situ of the cervix, where discontinuation is at the discretion of the investigator.)
- Subject is significantly noncompliant with study procedures.
- Occurrence of one or more of the following hepatic test abnormalities (confirmed on a second separate sample):
  - ALT or AST > 8 × ULN;
  - ALT or AST > 5 × ULN for more than 2 weeks;
  - ALT or AST > 3 × ULN and Total Bilirubin > 2 × ULN or international normalized ratio [INR] > 1.5;
  - ALT or AST > 3 × ULN with the appearance of fatigue, nausea, vomiting, right upper quadrant pain or tenderness, fever, rash, and/or eosinophilia (> 5%).

For subjects to be considered lost to follow-up, reasonable attempts must be made to obtain information on the subject's final status. At a minimum, 2 telephone calls must be made and 1 certified letter must be sent and documented in the subject's source documentation.

AbbVie may terminate this study prematurely, either in its entirety or at any site. The investigator may also stop the study at his/her site if he/she has safety concerns. If AbbVie terminates the study for safety reasons, AbbVie will promptly notify the investigator.

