## 5.6 Follow-Up for Subject Withdrawal from Study

---

To minimize missing data for efficacy and safety assessments, subjects who prematurely discontinue study drug treatment should continue to be followed for all regularly scheduled visits, unless subjects have decided to discontinue study participation entirely (withdrawal of informed consent). Subjects should be advised on the continued scientific importance of their data even if they discontinue treatment with study drug early.

Subjects who prematurely discontinue study drug should complete a PD Visit as soon as possible, preferably within 2 weeks of discontinuation. Samples for PK and immunogenicity will be collected during the PD Visit. Afterwards, subjects should follow the regular visit schedule as outlined in the Activity Schedule ([Appendix D](#)) and adhere to all study procedures except for dispensing study drug, PK sample collection and blood sample collection for optional exploratory research. Once the subject has discontinued study drug, all rescue- and efficacy-driven discontinuation criteria no longer apply. If at any point a subject no longer wants to provide assessments (withdrawal of informed consent) following discontinuation of study drug, a second PD visit is not required.

In addition, if subject is willing and has not withdrawn consent, a follow-up phone call 20 weeks after the last dose of study drug may be completed to ensure all treatment-emergent AEs/SAEs have been resolved.

All attempts must be made to determine the primary reason for discontinuation of study drug or study participation. The information will be recorded on the appropriate eCRF page. However, these procedures should not interfere with the initiation of any new treatments or therapeutic modalities that the investigator feels are necessary to treat the subject's condition. Following discontinuation of study drug, the subject will be treated in accordance with the investigator's best clinical judgment, irrespective of whether or not the subject decides to continue participation in the study.

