### 8.2 Ethical Conduct of the Study

---

The study will be conducted in accordance with the protocol, Operations Manual, International Council for Harmonisation of Technical Requirements for Pharmaceuticals for Human Use (ICH) guidelines, applicable regulations, and guidelines governing clinical study conduct and the ethical principles that have their origin in the Declaration of Helsinki. Responsibilities of the investigator are specified in [Appendix B](#).

In the event of a state of emergency due to the COVID-19 pandemic leading to difficulties in performing protocol-specified procedures, AbbVie will engage with study site personnel in efforts to ensure the safety of subjects, maintain protocol compliance, and minimize risks to the integrity of the study while trying to best manage subject continuity of care. This may include alternative methods of assessments (e.g., phone contacts or virtual site visits), alternative locations for data collection (e.g., use of a local laboratory instead of a central laboratory), study visit schedule modification, and home IP administration by trained site personnel to ensure continuity of treatment, where allowed. Refer to the Operations Manual in [Appendix F](#) for additional details. In all cases, these alternative measures must be allowed by local regulations and permitted by IRB/IEC. Investigators should notify AbbVie if any urgent safety measures are taken to protect the subjects against any immediate hazard.

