- If the **TB screening test** (either PPD or the QuantiFERON-TB Gold test [or IGRA equivalent]) is **positive**, or if there is a **repeat indeterminate** QuantiFERON-TB Gold test (or IGRA equivalent) upon retesting, subjects may participate in the study if **further work-up** (according to local practice/guidelines) establishes conclusively that the patient has no evidence of active TB.
- If the subject is diagnosed with **active TB**, the subject should not be randomized in the study and should not receive study drug. Subject will be considered as a **screening failure**.

- If presence of **latent TB** is established, subjects are not required to be treated with prophylactic anti-TB therapy prior to or during the study, if considered low risk for reactivation per investigator judgment.
- If the subject is diagnosed with **active TB** after being randomized, the subject should not receive any further study drug and follow the PD Visit procedure (Section 2.2).
- If **TB (latent or active)** is diagnosed during the study, it is also necessary to report it as an AE in the source documents and eCRFs. In the case of a TB-related AE, a TB supplemental form that provides additional information will be completed by the investigator or designee.

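### Operations Manual 3.12 takes pregnant subjects out of the study, while Protocol 5.5 and 5.6 stop study drug only and keep the scheduled visits

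*Protocol*

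**What the plan says.** Protocol 5.5 opens its list with "A subject will be discontinued from study drug at any time for reasons including but not limited to the following", and one item on that list is "Subject becomes pregnant while participating in the study". Protocol 5.6 then states that "subjects who prematurely discontinue study drug treatment should continue to be followed for all regularly scheduled visits", with withdrawal of consent as the only exception. Protocol 4.1 gives the same rule and names both safety and efficacy assessments. The Pregnancy paragraph of Protocol 6.1 says that such subjects must be discontinued and points to Section 5.5, but does not say from what.

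Operations Manual 3.12, under Pregnancy Tests, begins with "A pregnant or breastfeeding female will not be eligible for participation or continuation in this study". It ends by telling the site to withhold dosing after a positive urine test and run a serum test, and then adds "Pregnant subjects must discontinue from the study".

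Protocol 8.2 makes both texts binding: "The study will be conducted in accordance with the protocol, Operations Manual" and the applicable guidelines. Nothing in the documents provided says which prevails if they differ.

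**The concern.** Under the protocol, a pregnant subject stops drug and keeps coming to visits. Under the manual, her participation ends. A coordinator with a positive test in hand is likely to turn to the manual's testing section, and that section does not refer to Protocol 5.5 or 5.6.

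At stake is the scheduled adverse event, laboratory and vital-sign follow-up of a woman who may have received risankizumab. Knowledge of the pregnancy itself is not at stake.

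**Working it through.** The plan gives no figure on this point to reproduce. The check compares the texts and then does date arithmetic.

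**Which text is out of line.** Three things point to the manual.
- Protocol 6.1, the dedicated pregnancy text, refers to 5.5, which concerns study drug.
- In the manual's pregnancy text, withholding the dose is already covered in the sentence before, so leaving the study reads as a further step.
- The manual's TB Screening text, also in 3.12, handles another Protocol 5.5 reason correctly. For active TB after randomization, "the subject should not receive any further study drug and follow the PD Visit procedure".

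**Inputs.**
- Post-baseline visits at Weeks 2, 4, 10, 16, 20, 24, 28, 40 and 52 (Protocol Appendix D).
- Doses at Weeks 0, 4, 16, 28 and 40 (Operations Manual 6.1).
- Adverse event window of 140 days = 20 weeks after the last dose (Protocol 7.4, SAP 9.2.1).
- PD visit preferably within 2 weeks of stopping (Protocol 5.6).

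**Assumptions.** The test is positive at a dosing visit, that dose is withheld, the PD visit takes place 2 weeks later, and there is no contact after that.

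**Formulas.** Window end = week of last dose + 20. Unobserved weeks = window end − (week found + 2). Visits lost = scheduled visits after the week found.

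| Found at | Last dose | Visits lost | Window end | PD visit | Unobserved |
|---|---|---|---|---|---|
| Week 4 | Week 0 | 10, 16, 20, 24, 28, 40, 52 = 7 | 0 + 20 = 20 | Week 6 | 20 − 6 = 14 weeks |
| Week 16 | Week 4 | 20, 24, 28, 40, 52 = 5 | 4 + 20 = 24 | Week 18 | 24 − 18 = 6 weeks |
| Week 28 | Week 16 | 40, 52 = 2 | 16 + 20 = 36 | Week 30 | 36 − 30 = 6 weeks |
| Week 40 | Week 28 | 52 = 1 | 28 + 20 = 48 | Week 42 | 48 − 42 = 6 weeks |

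In days this is 14 × 7 = 98 or 6 × 7 = 42 of 140. A pregnancy first found at Week 52 costs no scheduled visit.

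**Efficacy.** A subject removed before Week 16 has no Week 16 assessment. Under NRI-C (SAP 8.2) she counts as a non-responder. One subject is 1/62 = 1.6 percentage points in a risankizumab arm or 1/31 = 3.2 points in the placebo arm, and the result changes only if she would otherwise have been a responder. A pregnancy found at Week 16 leaves that endpoint intact if the visit's assessments are done. The observed-case summaries in Period B already drop values after study drug is stopped.

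**Adverse event rates.** SAP 9.2.4 adds 140 days to every subject's exposure, so the unobserved weeks would still count in the denominator. With so few subjects the effect is tiny.

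**The case against.** The best defence is that the manual's sentence is loose wording for stopping drug. The manual is Appendix F of the protocol and not a rival document. Protocol 6.1 leads to 5.5, and 5.5 leads to continued visits. The documents blur the two ideas elsewhere: the drug-stop list in Protocol 5.5 itself speaks of withdrawal from the study, and Operations Manual 3.12 uses study discontinuation for a significant laboratory result. This is probably what was intended, and it limits the severity. It does not remove the conflict, because the pregnancy text bars continuation in its first sentence and requires leaving the study in its last.

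Three stronger readings are tempting, and the documents do not support them.

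- *The safety record of a pregnant subject is lost.* Protocol 6.1 and Operations Manual 4.1 still require adverse events to be collected to 140 days. Protocol 6.1 still requires the pregnancy to be reported within one working day and its outcome to be collected. Counting every day from discovery as lost (112 or 56) also ignores the PD visit.
- *Protocol 5.6 waives the 20-week call.* It says that "a follow-up phone call 20 weeks after the last dose of study drug may be completed to ensure all treatment-emergent AEs/SAEs have been resolved", but this depends on the subject being willing and not having withdrawn consent. The retained visits often make the call redundant: for the first two rows of the table the window ends at the Week 20 or Week 24 visit, and for the last two the Week 40 or Week 52 visit falls after it closes and can look back.
- *The lack of a pregnancy prompt after Week 52 is an error.* Protocol 5.1 asks for contraception to at least 140 days after the last dose, but nothing requires testing for that long, and a pregnancy that the site learns of must be reported.

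**Conclusion.** The conflict is real and Operations Manual 3.12 is the text to correct. Severity is minor. The cost is 1 to 7 scheduled visits for a pregnancy found at a post-baseline dosing visit, and about 14 or 6 weeks without scheduled observation. Those weeks rest on a PD visit at two weeks and no other contact, which the continuing collection duties make less likely.

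The documents give no expected number of pregnancies; few are likely, given the contraception requirement. The efficacy effect is tiny but not nil, because of the Week 16 non-responder rule. Sample size, power and alpha are untouched.

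**What to change.** - Operations Manual 3.12, Pregnancy Tests, last sentence: *Pregnant subjects must discontinue study drug and be followed per Protocol Sections 5.5 and 5.6.*
- Same text, first sentence: limit it to eligibility and continued dosing.
- Protocol 6.1, Pregnancy: *must be discontinued from study drug (Section 5.5).*

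The criteria for stopping drug do not change. The cost is three wording edits and, for each pregnant subject, up to seven further visits with routine blood draws (and TB testing at Week 52 if she has had no prior positive test), which she may decline.

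Two optional extras, neither correcting an error, are firmer wording for the 20-week call in Protocol 5.6 and a pregnancy question on the follow-up call in Operations Manual 2.2.
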